11.1 Data Recording/Reporting

Data generated from laboratory testing of organoids will be recorded and stored on computers at King's College London. Laboratory data will be linked to the participant through a participant trial number. No identifying information will be used on the samples or when used in the laboratory. The data obtained from the laboratory tests will not be used for clinical purposes and will not be reported to the clinical team. Separate diagnostic testing will be done by the clinical teams as per normal processes.

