This study aims to address the hypothesis that it would be possible to generate patient-derived organoids (PDOs) from resected brain or resected/biopsied extra-cranial metastases and to collect preliminary data on the ability of PDOs to predict patients' treatment response and their radiosensitivity and chemosensitivity can be correlated with their survival outcome.

Patient cohorts

- 1) Breast cancer patients with brain metastases undergoing surgical resection with or without further radiotherapy (SRS or whole brain radiotherapy)
- 2) Breast cancer patients with extra-cranial metastases undergoing surgical resection or biopsy

Primary objective

To assess the percentage of successful generated organoids from resected brain or resected/biopsied extra-cranial metastases of breast cancer patients

Secondary objectives

- 1) To assess the sensitivity of radiotherapy in PDOs

- 2) To assess the sensitivity of the same systemic treatments that the patients previously had and will have in PDOs
- 3) To correlate the treatment sensitivities of PDOs above with the treatment outcome of patients
- 4) To correlate IC50 doses/dose response curves above with the objective response rates of patients undergoing same systemic treatment

Exploratory objectives

- 1) To assess and correlate the histopathological (including immune markers), genomic and transcriptomic features of patients' samples with PDOs
- 2) To assess peripheral immune responses in patients before and after radiation +/- systemic treatments and to correlate the results with those in PDOs
- 3) To assess the sensitivities of PDOs to various targeted therapies based on their genomic profiles and mutations
- 4) To assess the novel treatment combination of radiotherapy with immunotherapy and other agents in patient-derived organoids co-cultured with immune cells
- 5) Collection of archival tissues, blood samples, saliva, oral swab, cerebrospinal fluid (CSF), urine or stool samples for other translational research

8 Study design & Flowchart

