8.1 Study Design

This is a prospective observation study to establish the pathways required to successfully generate PDOs from resected brain or resected/biopsied extra-cranial metastases and to test their treatment sensitivity in correlation with patients' treatment outcomes. In addition, the time required to generate organoids and to assess treatment response in order to correlate with patients' outcome will be evaluated.

Endpoints

This main endpoint is the success rate in generating PDOs from brain or extra-cranial metastases of breast cancer patients.

Primary endpoint

The percentage of individuals whose successful organoid samples from metastases are obtained

Secondary endpoints

- 1) To determine the IC50 doses and dose response curves of radiotherapy
- 2) To determine the IC50 doses and dose response curves of the previous and same systemic treatments that patients had or will have in PDOs

- 3) To correlate the IC50 doses and dose response curves above with the recurrence rates and progression-free survival of patients
- 4) To correlate IC50 doses/dose response curves above with the objective response rates of patients undergoing same systemic treatment

Exploratory endpoints

- 1) Tumour immune markers (including CD4 and CD8 T cells, FoxP3, PDL1), exome sequencing and RNA sequencing of PDOs and patients' samples
- 2) Peripheral immune responses (including CD8-T cell with exhaustion and cytolytic activity marker, CD4/FoxP3 Tregs) in patients before and after radiation +/- systemic treatments and correlation of the results with those in PDOs
- 3) The IC50 doses of various targeted therapies based on actionable genetic mutations + cell viability data of PDOs
- 4) The promising treatment combination of radiotherapy with immunotherapy and other agents in PDOs co-cultured with immune cells
- 5) To conduct further translational research using the patients' samples including assessing plasma and CSF ctDNA before and after treatments in patients

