11.2 Sample Receipt/Chain of Custody/Accountability

A member of the research team will collect the samples and process them in [name] at KCL. Tumour tissues will be processed for organoid cultures and blood samples processed for PBMC and plasma storage. CSF will also be processed for storage at [name] laboratory. Processed blood samples (PBMC isolates and plasma), and processed CSF, along with all other samples (saliva, oral swab, urine and stool) will be given to the biobank at Guy's Hospital for storage. The receipt, processing and transfer of samples will be documented through Sample Processing Forms. Upon receipt of the tumour samples, the laboratory will ensure that the physical integrity of these samples have not been compromised in transit. If it has, it is important that the study teams, as well as the sponsor, are informed of this. Tumour samples will be processed for organoid cultures and will be kept in [name] laboratory for the duration of the study and frozen for long-term storage. Upon receipt of samples laboratory staff will ensure that all samples are accounted for as per the labeling. All samples received will be logged in a study sample log.

Samples will be transferred on foot at the Guy's campus between Guy's Hospital and New Hunt's House. Samples will be transferred using the KHP staff bus when collecting samples from KCH.

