14.1 Data management

As this is an observation study, we will only be collecting data from patients that are already available in the hospital record on patients' demographics, menopausal state, tumour characteristics (including ER/PR and HER2 status), previous treatments and proposed treatment plans. The patients' treatment details, treatment responses, recurrences and survivals will also be obtained from clinical record. The data will be recorded on paper Case Report Forms (CRFs). Participant files and paper CRFs will be identified using a Participant Identification Number. Personal information will not be stored on CRFs. Data will be entered into an electronic CRF database (Excel) designed by the research team and stored on secured servers at King's College London. Access to the database will be granted by the Chief Investigator.

Screening and enrolment logs will be maintained by the research team. For enrolled participants, identifiable patient data will be stored in an Excel file for the purposes of gathering follow-up data. This file will password protected and stored on the GSTT secured network, whereby access is only granted by the site PI to named individuals.

Consent forms and an Investigator Site File will be kept at the recruiting sites. Paper CRFs, copies of consent forms and the Trial Master File will be stored in locked filing cabinets within the [name] (KCL, Guy's Campus) and the Oral Clinical Research Unit (KCL, Guy's Hospital, London, UK).

Data generated from laboratory processes related to the generation of PDOs and subsequent testing will be kept in the research laboratory. These data will be identified with the PIN and no personal data will be used in the lab records.

Data linkage

If the participating patients have come from or will move to different health care providers, we will attempt to get either available archival tissues and/or data from the relevant health care providers after sending them the relevant patients' consent forms. We may also go to the central national databases with a patient's NHS number to get clinical data if necessary.

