Full dataset and linked code with patient identifiers will be kept for 5 years at local recruiting sites for governance purposes on Trust networks. This dataset will be accessed by the research team for long term follow-up of participants for up to 5 years of their recruitment to the study. Subsequently identifiable data will be deleted (name, NHS/hospital number and date of birth). A pseudonymised dataset will be kept for 5 years after study completion at King's College London which will link participant trial numbers to their age at consent, ethnicity, gender, clinical information and treatment outcome.

15 Statistical considerations

The first year of recruitment will serve as a pilot study for this observation study and no formal power calculation is performed for year 1. We expect more than 50% of the approached participants will consent to taking part in SOTO-BC study and at least 30% of the tissue samples will be successfully

used to generate organoids. A successful pilot study will be defined as one that meets the pre-defined expectation. The data from study will be used to calculate the sample size required to extend the observation study, which will be submitted as a major amendment.

16 Ethical considerations

16.1 *Research Ethics Committee (REC) review & reports*

Before the start of the trial, approval will be sought from an NHS REC for the trial protocol, informed consent forms, patient information sheet, and GP information letters.

Any amendments to the protocol or study documents will be reviewed by the Sponsor, sent to the REC for review and approvals. No changes will be implemented until approval has been received from the REC and approved by the Trust R&D department, if required.

All correspondence with the REC will be retained in the Trial Master File.

An annual progress report (APR) will be submitted to the REC within 30 days of the anniversary date on which the favourable opinion was given, and annually until the trial is declared ended. The Chief Investigator's will approve the annual report, which will be submitted by the CI or delegate.

The Chief Investigator will notify the REC of the end of the trial within 90 days of the end of the study. If the trial is ended prematurely, the Chief Investigator will notify the REC, including the reasons for the premature termination.

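### Secondary endpoints 3 and 4: PDO results are withheld from clinicians, but outcomes are not withheld from assay readers, and no rule fixes the PDO readout before the outcome is known

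*Protocol*

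**What the plan says.** The only masking rule is in section 11.1 and runs from laboratory to clinic: "The data obtained from the laboratory tests will not be used for clinical purposes and will not be reported to the clinical team". For the laboratory, the same section offers pseudonymisation: "No identifying information will be used on the samples or when used in the laboratory". It also states that "Laboratory data will be linked to the participant through a participant trial number".

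On who handles what, section 11.2 says "A member of the research team will collect the samples and process them". Section 14.1 says "The patients' treatment details, treatment responses, recurrences and survivals will also be obtained from clinical record" and, of the dataset kept with patient identifiers, "This dataset will be accessed by the research team for long term follow-up of participants".

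On timing, section 10.1 has organoids tested once they hold enough cells, using treatments the patient has had or is going to have. Section 11 keeps the organoids frozen after the experiments for later work. Section 8.1 adds that "the time required to generate organoids and to assess treatment response in order to correlate with patients' outcome will be evaluated".

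On purpose, section 7 aims "to collect preliminary data on the ability of PDOs to predict patients' treatment response". Secondary endpoint 3 relates the radiotherapy and systemic-treatment readouts, past treatments included, to recurrence and progression-free survival. Endpoint 4 relates them to objective response.

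**The concern.** A claim that an assay predicts outcome needs two protections. The outcome must be judged without knowledge of the assay, and the assay must be read without knowledge of the outcome, or at least be fixed before the outcome occurs. The protocol gives the first and not the second.

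Without the second, whether a run is accepted, repeated or refitted can be influenced by knowing how the patient fared, and any such influence tends towards agreement. Separately, a readout obtained after the response is known can show concordance but cannot show prediction, however carefully it was made. If both kinds are pooled in endpoint 3, the pilot cannot say how much of an observed correlation is prospective.

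The pilot data are also meant to inform the sample size of the extension (section 15). If these correlations enter that calculation, which the protocol does not specify, an inflated one would make the next study too small.

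**Working it through.** The protocol states no figure on this point, so there is nothing to reproduce. The check sets the relevant passages side by side.

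1. **Direction of masking.** Section 11.1 withholds laboratory results from clinicians. The nearest text in the other direction removes identifiers from samples and laboratory work. That conceals who the patient is but does not withhold the outcome, and the trial number links the two sets of data.

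2. **Separation of people.** Section 11.2 gives sample processing to a member of the research team. Section 14.1 gives the research team access to the follow-up dataset. The protocol does not say that the same individuals do both, but it has no rule that keeps them apart.

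3. **What the laboratory must know.** To test the treatments a patient had or will have (section 10.1), the laboratory needs the list of treatments. It does not need the results of those treatments, and the protocol does not draw that line.

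4. **Order in time: past treatments.** Previous treatments are part of secondary objective 2 and endpoint 2, and endpoint 3 refers back to those readouts. For a completed treatment, the response can be known before the tissue is even cultured. This follows from the design and needs no assumption about turnaround.

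5. **Order in time: future treatments.** Testing depends on cell numbers, with no date and no order relative to the response assessment. Frozen stocks make late or repeat readouts possible. The time needed to generate and test organoids will be evaluated (section 8.1), but the protocol does not use it to sort pairs into those read before and those read after the outcome.

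6. **Scale.** Inputs are 20 patients (section 10.1) and at least 30% success (sections 10.6 and 15). With one sample per patient assumed, 20 × 0.30 = 6 organoid lines. For any one future treatment, the number read after the outcome could lie anywhere from 0 to 6, because no turnaround is stated.

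7. **Closest time scale in the protocol.** For resected brain metastases, section 6.1 quotes median surgical-bed relapse-free survival of 7.5 and 7.7 months and median overall survival of 12.2 and 11.6 months. If those medians carried over, about half of such patients would still be free of surgical-bed relapse at about 7.5 months. With a turnaround shorter than that, at least half of the pairs could be prospective for that outcome. Objective response and progression elsewhere may come earlier, and section 10.5 leaves imaging to routine care.

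**The case against.** The case for leaving the text alone has real parts.

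- **Purpose.** This is a feasibility pilot (section 12.2) whose primary endpoint is organoid success. None of the progression criteria in section 10.6 depends on endpoints 3 and 4. Section 7 asks only for preliminary data on prediction, and the endpoints themselves speak of correlation. This stands and limits the point to those two secondary endpoints.
- **Other documents.** Section 11 refers further detail on processing and analysis to a laboratory manual that is not shown. Run acceptance, repeats and curve fitting may be defined there or in an analysis plan. This stands for those details. Who is masked, and whether the readout must precede the outcome, are design features, and section 11.1 already sets one half of the masking in the protocol.
- **Existing controls.** Laboratory data stay in the laboratory under the participant number, the Chief Investigator grants access to the database, and the identifiable follow-up file is limited to named individuals (section 14.1). These are confidentiality controls and do not mask assay readers to outcome.

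A reader might also infer more than the text supports:

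- That organoids could be matched to patients after the event. They cannot, because the trial number fixes the match and endpoint 4 states the same-treatment rule.
- That most outcomes would precede the readout, from the 3.7-month median survival quoted for triple-negative disease in section 6.1. That figure is from a general brain-metastasis series, and the figures for resected patients are much longer.
- That 1/6 = 17% measures the bias from one altered readout. It is only that readout's share of six pairs.
- That the gap carries a calculable error rate. Choosing the best of 2 readouts × 3 outcomes at an assumed 0.05 gives 1 − 0.95^6 = 0.265 if independent, and down to about 0.15 if correlated. That is multiplicity, and locking the readout would not remove it.

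**Conclusion.** The point holds for secondary endpoints 3 and 4 and does not touch the primary endpoint. Masking runs one way, and the protocol does not require the organoid readout to be fixed before the outcome is known. As written, the plan will mix readouts made after a known response, certainly possible for past treatments, with prospective ones, under an aim worded as prediction.

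The direction of any bias is towards agreement. Its size cannot be given, because it depends on assay turnaround and on how runs are accepted, and the protocol states neither. About 6 organoid lines are at stake at the 30% criterion, assuming one sample per patient. The documents do not show that any readout would in fact be altered; they show only that nothing prevents it. The change is worth making now, because masking cannot be restored once outcomes are known.

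**What to change.** In sections 11.1 and 14.1, state that:

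- those who run or read the organoid assays receive the list of treatments to test but do not see response, recurrence or survival data;
- each quality-checked readout (IC50 and curve, per participant and treatment) is dated and locked in the laboratory record before that participant's outcome is linked to it;
- later reruns are logged and do not replace the locked result.

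In endpoints 3 and 4, report two groups separately: (a) future treatments whose locked readout predates the response assessment or progression, and (b) past treatments together with readouts locked afterwards. Base any statement about prediction on group (a) only. Group (b) remains useful as evidence of concordance.

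The cost is a date field and a lock step. These belong in the laboratory record, where section 14.1 keeps the organoid data, and not only in the clinical Excel database. No extra staff, assay or visit is needed, and patient care does not change. The real downside is that, out of about six organoid lines, fewer pairs will support a predictive statement.

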11.2 Sample Receipt/Chain of Custody/Accountability

A member of the research team will collect the samples and process them in [name] at KCL. Tumour tissues will be processed for organoid cultures and blood samples processed for PBMC and plasma storage. CSF will also be processed for storage at [name] laboratory. Processed blood samples (PBMC isolates and plasma), and processed CSF, along with all other samples (saliva, oral swab, urine and stool) will be given to the biobank at Guy's Hospital for storage. The receipt, processing and transfer of samples will be documented through Sample Processing Forms. Upon receipt of the tumour samples, the laboratory will ensure that the physical integrity of these samples have not been compromised in transit. If it has, it is important that the study teams, as well as the sponsor, are informed of this. Tumour samples will be processed for organoid cultures and will be kept in [name] laboratory for the duration of the study and frozen for long-term storage. Upon receipt of samples laboratory staff will ensure that all samples are accounted for as per the labeling. All samples received will be logged in a study sample log.

Samples will be transferred on foot at the Guy's campus between Guy's Hospital and New Hunt's House. Samples will be transferred using the KHP staff bus when collecting samples from KCH.

11.3 Sample Transfer to sites outside the Organisation

Individual informed consent will be obtained from the patients to specify whether they would agree for their samples to be transferred to collaborating third parties including overseas and commercial laboratories on behalf of KCL. This may include but not be limited to validation of research results.

The patient samples and derived organoids (with linked data) may be shared with collaborating laboratories, nationally or internationally, for the purposes of facilitating the research aims. Specific agreements will be put in place as required by the Sponsor including material transfer agreements where necessary. Any commercialisation of the results of this study will be specified in contractual arrangements between parties where necessary and participants will be informed that they would not benefit financially.

12 Assessment of Safety

This is an observation study and the patients participated in this study will undergo routine treatments and the safety of the treatments will be assessed as per standard of care. No serious adverse events are expected to occur following the tissue sampling involved in this study, as they will be done during standard care procedures. Participants will be followed-up by their treating clinicians as per normal practice.

12.1 Ethics Reporting

Annual progress reports will be submitted to the Research Ethics Committee as per normal regulatory processes.

12.2 Trial Steering Committee

No formal trial steering committee will be set up for this feasibility study.

12.3 Ethics & Regulatory Approvals

Study protocol and other documentation will be submitted to the North East - Tyne & Wear South Research Ethics Committee (REF 24/NE/0022) for ethical approval.

13 Compliance and withdrawal

13.1 Subject compliance

We will monitor the percentage of approached participants who consent to taking part in the study during the first year of recruitment.

13.2 Withdrawal / dropout of subjects

The right of a participant to refuse participation without giving reasons will be respected. The participant will remain free to withdraw at any time from the trial without giving reasons and without prejudicing his/her further treatment and will be provided with a contact point where he/she may obtain further information about the trial. Patients will be made aware of the terms and conditions around withdrawal. If a patient withdraws from the study, the research team can retain any tissue samples, DNA/RNA samples and organoids/cell lines that have been created up until the time of the patient's withdrawal if the patient agrees. Any unused samples taken for research purpose can be destroyed if patient requests to do so. Any demographic and medical information already provided or results from tests already performed on their samples will continue to be used in the study, however no further data or sample collection will be performed. If a participant consents to the study but subsequently loses the capacity to consent during the study, we will withdraw the participant from sample collection. However, we will retain and make further use of any identifiable data and collected tissues until the point of withdrawal. We will stop taking any further blood or other samples from the participant although we will continue collecting information about the participant's health from the hospital record and/or GP for up to 5 years.

We will monitor the percentage of participants who withdraw consent from the study after taking part. If no longer wishing to take part, participants will consent to have their collected samples and data included in the research after they have withdrawn and to consent to follow their clinical outcomes through their medical notes. The patient recruitment for the pilot study will last 18 months with additional follow-up for another 12 months. If there is withdrawal of consent from any patients before the organoids are successfully generated from the samples, we will recruit more participants to back fill those who may have withdrawn or dropped out, provided that this is within the recruitment period stated above.

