10.6 End of Study Definition

The patient recruitment for the pilot study will last 18 months and the follow-up period for additional sample collection will last another 12 months. We will assess whether the endpoints and outcomes are met but the patients will be followed up for their long-term treatment outcome and survival for up to 5 years. The end of the study definition for the pilot study is the end of the 30 months' period after the commencement of the study regardless of the number of patients recruited. We will submit the protocol for a substantial amendment approximately 1 year after the recruitment of the first participant so that the SOTO-BC study will continue as a prospective observation study for up to additional 3 years including further recruitment or as a new main study if funding is obtained. If no funding is obtained by the end of 18 months, we will end the patient recruitment and continue to collect samples from recruited patients for 12 months.

In addition to obtaining funding, the criteria for progression beyond pilot study are set as below:

- 1) More than 50% of the approached participants will consent to taking part in SOTO-BC study
- 2) At least 30% of the tissue samples will be successfully used to generate organoids
- 3) Further funding is obtained to continue beyond the 18-month recruitment period

11 Laboratories and sample storage

The fresh tissue samples will be processed for organoids within 24 to 48 hours of surgery/biopsy. Once the experiments on the organoids have been completed, they will be frozen for future analysis and stored in [name] laboratory at KCL. Blood samples will be processed according to standard laboratory SOP in [name] (KCL, London, UK) for PMBCs and plasma collection. Plasma and/or CSF samples will also be processed to assess ctDNA in the future. The additional biological samples including saliva, oral swab, urine or stool samples if obtained will be stored at Guy's Hospital biobank. Once collected, these samples will be stored directly with the biobank. All unused samples will be stored for 5 years from the end of the SOTO study under the biobank's HTA license (reference 12121, Designated Individual [name]). At the end of this storage period, the unused biological samples stored at Guy's biobank will be handled and/or destroyed according to the biobank's Standard Operating Procedure (SOP) if the agreement to store the samples has expired and/or not extended.

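### Does back-filling withdrawals until organoids succeed let known culture failures be replaced and inflate the success rate?

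*Protocol*

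**What the plan says.** Section 13.2 provides for back-filling after "withdrawal of consent from any patients before the organoids are successfully generated from the samples, we will recruit more participants to back fill" the places of those who withdrew or dropped out, "provided that this is within the recruitment period stated above". The period is given in the same section: "The patient recruitment for the pilot study will last 18 months with additional follow-up for another 12 months".

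Section 13.2 also says what happens to material from someone who has withdrawn. On data, "results from tests already performed on their samples will continue to be used in the study". On samples and data together, "participants will consent to have their collected samples and data included in the research after they have withdrawn". There is a limit: tissue and organoids are kept if the patient agrees, and "Any unused samples taken for research purpose can be destroyed if patient requests to do so".

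The primary endpoint in section 8.1 is "The percentage of individuals whose successful organoid samples from metastases are obtained". The second progression criterion in section 10.6 is "At least 30% of the tissue samples will be successfully used to generate organoids". Section 10.1 sets the target at 20 patients, and section 15 states that no formal power calculation was made. No section says whether a replaced participant counts in the denominator.

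**The concern.** A replacement rule should not depend on the outcome being measured. This one closes when the culture succeeds, not when its outcome is known. A failed culture never reaches success, so that participant can be replaced on withdrawal at any time until recruitment closes. A participant with a successful culture cannot. Failures are therefore exposed to replacement for longer than successes, even if withdrawal has nothing to do with the culture result.

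If each replaced participant were also left out of the analysis, failures would be removed more often than successes and the rate would drift upward. With about 20 patients and a fixed 30% cut-off for progression, a culture technique somewhat below the threshold would pass more often than it should. Section 12.2 provides no formal steering committee to catch this.

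**Working it through.** The protocol gives no power, error rate or withdrawal rate, so there is no stated figure to reproduce. The check has three steps.

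**1. What the text implies for the denominator.** A culture that has failed is a result already obtained. The retention sentences in section 13.2 keep such results in use. The back-fill sentence asks for further recruitment and says nothing about deleting a record. The two are compatible: the failure stays, one more patient is recruited, and the number analysed rises above 20.

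**2. The rate if known failures are kept.** Let p be the true success rate and w the share of failures later withdrawn and replaced. Patients are drawn until 20 non-replaced outcomes are reached, and the rate is successes divided by everyone cultured, replaced failures included. Mean of 100,000 simulated trials:

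| p | w = 10% | w = 20% | w = 30% |
|---|---|---|---|
| 0.30 | 30.1% | 30.2% | 30.3% |
| 0.25 | 25.1% | 25.2% | 25.3% |

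The residual 0.1 to 0.3 points comes from averaging a ratio with a random denominator. The chance of reaching 30% does not rise. At p = 0.30 it falls from 0.584 to about 0.51 at w = 10%. Much of this is rounding: 6 of 20 is exactly 30%, but with 21 patients 0.30 × 21 = 6.3, so 7 are needed.

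**3. The rate if known failures were dropped (the adverse case, which the text does not state).** Assumptions: withdrawal is unrelated to outcome, entry is uniform over 18 months, the culture outcome is known at 2 months, and there is one sample per patient. For yearly withdrawal rate r, the monthly hazard is h = −ln(1 − r)/12. Let ds and df be the shares of successes and failures that withdraw while replaceable. Each is the average over entry times of 1 − exp(−h × exposure). Exposure is min(2, 18 − entry) months for successes and 18 − entry months for failures. Then

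observed rate = p(1 − ds) / [p(1 − ds) + (1 − p)(1 − df)].

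Example at r = 5%: h = 0.00427, ds = 0.0080, df = 0.0375. At p = 0.30 this gives 0.30 × 0.9920 = 0.2976 and 0.70 × 0.9625 = 0.6738, so the rate is 0.2976/0.9714 = 0.3064.

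| r per year | ds | df | reads, p = 0.30 | reads, p = 0.25 | P(≥6 of 20), p = 0.30 | P(≥6 of 20), p = 0.25 |
|---|---|---|---|---|---|---|
| 0 | 0 | 0 | 30.0% | 25.0% | 0.584 | 0.383 |
| 2% | 0.0032 | 0.0150 | 30.2% | 25.2% | 0.593 | 0.392 |
| 5% | 0.0080 | 0.0375 | 30.6% | 25.6% | 0.608 | 0.406 |
| 10% | 0.0164 | 0.0750 | 31.3% | 26.2% | 0.632 | 0.430 |
| 20% | 0.0345 | 0.1501 | 32.8% | 27.5% | 0.683 | 0.483 |
| 30% | 0.0545 | 0.2256 | 34.4% | 28.9% | 0.735 | 0.542 |

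For scale, the standard error at p = 0.30 and n = 20 is √(0.30 × 0.70/20) = 0.102.

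The bias comes from failures already known at withdrawal, which are 78%, 77% and 76% of the failures removed at r = 10%, 20% and 30%. These are the results that section 13.2 says continue to be used.

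**The case for a change.** The strongest case for a change is that the trigger is an enrolment rule fixed in the protocol, which an analysis plan cannot rewrite. A systematic shift is not excused by being smaller than sampling error, and two sentences would make the trigger neutral. Keeping failures is also only an inference. Retention of tissue is conditional on the patient's agreement, and unused samples can be destroyed. At 20 to 30% yearly withdrawal the adverse case moves the rate by about 3 to 4 points.

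The literal asymmetry stands, and so does the arithmetic. The rest is weaker. Recruiting an extra patient does no harm by itself; only the denominator matters, and defining it is ordinary analysis-plan work. The conditions on tissue do not reach a failure already recorded, because the sentence on test results carries no such condition. They matter for cultures interrupted by withdrawal. If those were counted as failures the rate would move down: a true 30% reads p(1 − ds) = 29.5% to 28.4% at 10 to 30% a year. So the unstated counting rules do not even fix a direction.

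The high withdrawal rates have no support in the protocol. Section 10.1 requires no visits beyond standard care. Section 11.1 keeps laboratory results from the clinical team, so there is no evident route from a failed culture to a withdrawal. The 30% criterion also counts tissue samples, so replacing a participant does not on its face delete a sample already processed.

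**Conclusion.** The wording of the back-fill trigger is loose, but no change follows. An upward bias needs two things: withdrawal after a known failure within the 18 months, and removal of that failure from the denominator. The protocol states the second nowhere, and the retention sentences in section 13.2 point against it. Followed as written, the plan gives an essentially unbiased rate, with a simulated mean of 30.0 to 30.3% for a true 30% and 25.0 to 25.3% for a true 25%.

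In the adverse reading the shift is 0.2 to 0.6 points at 2 to 5% yearly withdrawal, which is plausible for a study without extra visits. It reaches 4.3 points only at an assumed 30% a year. These figures rest on the assumed withdrawal rates, uniform entry, a 2-month culture reading and one sample per patient. What remains is an unstated denominator rule, which analysts would fill by counting every determined culture and which an analysis plan would normally set out. In a 20-patient pilot, rewriting the trigger would change essentially no result.
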